## **9.10 PHARMACOKINETIC AND IMMUNOGENICITY ANALYSES**

### **9.10.1 PHARMACOKINETIC ANALYSES**

The PK analyses will be based on the PK analysis set, unless otherwise specified.

Plasma concentration data for JTX-2011 will be listed by subject and summarized in tables with standard descriptive statistics by analyte (Drug, i.e., JTX-2011, nivolumab, ipilimumab or pembrolizumab), Part, Dose Level, Cycle, and Time Point. Linear and log-linear plots of concentration versus time will be provided for individual subjects and for means by Drug, Part, Treatment (monotherapy or combination with nivolumab, ipilimumab, pembrolizumab), Dose Level, and Cycle.

PK parameters will be determined by NCA using a validated software platform (WinNonlin/Phoenix™ version 8.0 or higher). Actual sampling times will be used and the estimation method will be linear up, linear down. The analysis will be conducted by or under the oversight of the Clinical Pharmacologist at Jounce. Derived PK parameters will be provided to the statistical department at Jounce to be listed by subject and summarized in tables by Drug, Part, Treatment, Dose Level, and Cycle with descriptive statistics (n, mean, standard deviation, median, minimum, maximum and, for  $C_{max}$  and AUC parameters, geometric mean (geo mean) and geometric coefficient of variation (GCV%)).

$C_{max}$ ,  $T_{max}$ ,  $AUC_{last}$ ,  $C_{max}/D$  and  $AUC_{last}/D$  will be calculated for all subjects with evaluable concentration-time profiles. The terminal elimination rate constant ( $\lambda_z$ ) and parameters requiring  $\lambda_z$  for calculation ( $AUC_{inf}$ ,  $AUC_{inf}/D$ ,  $t_{1/2}$ ,  $CL_z$  and  $V_z$ ) will only be reported when at least 3 points on the terminal elimination phase (excluding  $C_{max}$ ) can be fit via log-linear regression to a line with an adjusted  $R^2$  value of  $\geq 0.9$ .

In cases where  $AUC_{inf}$  can be calculated, only values with extrapolated areas  $\leq 20\%$  will be included in summary tables and statistics. All  $AUC_{inf}$  values will be reported in the listings, but values with extrapolated areas  $> 20\%$  will be flagged and footnoted as not included in the summary statistics due to the large percentage of extrapolated area.

Additional PK analysis (population PK/PD modeling or exposure response analysis) may also be conducted and will be documented separately if done.

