1.4.2. JTX-2011 Schedule Determination

1.4.2.1. Rationale for Every 3 Week (q3w) Dosing

Pre-clinical PK and potency data supported up to a 3-week dosing interval. At the proposed highest dose of 1.0 mg/kg, sustained target engagement (greater than 95%) was predicted for the 3-week dosing interval.

Based on the preponderance of data, the proposed starting dose for Phase 1 is 0.003mg/kg and the proposed dose escalation schedule for the Phase 1, Part A is 0.003mg/kg, 0.01mg/kg, 0.03mg/kg, 0.1mg/kg, 0.3mg/kg, and 1mg/kg administered on a 21-day cycle.

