9.1.3. Pharmacokinetic Endpoints

PK endpoints are for JTX-2011 unless otherwise specified. The following PK endpoints will be determined (if feasible):

- Maximum observed concentration (C_{max}) of JTX-2011, nivolumab, ipilimumab and/or pembrolizumab in serum for all treatment cycles;
- Minimum measured concentration (C_{min}) of JTX-2011, nivolumab and/or pembrolizumab in serum for treatment cycles >1);
- Time from dosing to maximum measured concentration (t_{max});
- Area under the serum concentration-time curve over the dosing interval ($AUC_{0-\tau}$)

- Area under the serum concentration-time curve over the time interval from 0 to 336 hours after dosing (AUC_{0-336}) for nivolumab, in order to compare nivolumab PK to PK in literature in which nivolumab is dosed q2w);
- Area under the concentration-time curve of from time 0 extrapolated to infinity ($AUC_{0-\infty}$) JTX-2011, nivolumab, ipilimumab and/or pembrolizumab in serum over the time interval from 0 extrapolated to infinity);
- Percentage of $AUC_{0-\infty}$ obtained by extrapolation from the last evaluable time point ($\%AUC_{12-\infty}$);
- Terminal rate constant in serum (λ_z);
- Terminal half-life of JTX-2011 or nivolumab in serum ($t_{1/2}$);
- Mean residence time (MRT_{iv}) of JTX-2011, nivolumab, ipilimumab and/or pembrolizumab in the body after intravenous infusion);
- Total clearance (CL) of the analyte in serum after intravenous infusion;
- Apparent volume of distribution (V_z) during the terminal phase λ following intravenous infusion;
- Apparent volume of distribution at steady state following intravenous infusion (V_{ss}).
- Assess impact of ADA on PK

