## 8.2 PHARMACOKINETICS AND IMMUNOGENICITY DEFINITIONS AND ENDPOINTS

### 8.2.1 PHARMACOKINETICS

- PK will be evaluated by non-compartmental analysis (NCA). The table below defines the PK parameters that maybe derived from the NCA for this study.

Parameter Abbreviation	Definition	Unit	Dependence on $\lambda_z$
$C_{\max}$	Maximum observed plasma concentration	ng/mL	no
$T_{\max}$	Time when $C_{\max}$ is observed	days	no
$AUC_{\text{last}}$	Area under the drug concentration-time curve from time 0 to the time of the last quantifiable drug concentration	ng·days/mL	no
$AUC_{\text{inf}}$	Area under drug concentration curve from time 0 extrapolated to infinity	ng·days/mL	yes
$\lambda_z$	Terminal elimination rate constant	days 	NA
$t_{1/2}$	Terminal elimination half-life	days	yes
CL	Clearance of drug	L/day	yes
$V_d$	Volume of distribution	L	yes
$C_{\max}/D$	$C_{\max}$ normalized by dose	ng/mL/mg	no

AUC last /D	AUC last normalized by dose	ng·days/mL/ mg	no
AUC inf /D	AUC inf normalized by dose	ng·days/mL/ mg	yes

Parameters with no dependence on  $\lambda_z$  will be calculated for all subjects. Parameters with a dependence on  $\lambda_z$  will be calculated and reported as described in Section 9.10 Pharmacokinetic and Immunogenicity Analyses.

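### The 20% extrapolation limit is written for AUCinf alone, so AUCinf and the CL, Vz and AUCinf/D computed from it would be summarised on different subjects, and two fixed-interval AUCs in the protocol are missing from the SAP

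*SAP*

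**What the plan says.** SAP 9.10.1 handles the parameters that depend on the terminal rate constant λz in two steps.

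- AUCinf, AUCinf/D, t½, CLz and Vz share one reporting condition. They "will only be reported when at least 3 points on the terminal elimination phase", excluding Cmax, fit a log-linear regression with adjusted R² of at least 0.9.
- A second condition, extrapolated area of at most 20%, is then set for AUCinf. Larger values stay in the listings but "will be flagged and footnoted as not included in the summary statistics due to the large percentage of extrapolated area".

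Summarising is the default: "Derived PK parameters will be provided to the statistical department at Jounce to be listed by subject and summarized in tables by Drug". SAP 8.2.1 adds no other rule. It says that λz-dependent parameters "will be calculated and reported as described in Section 9.10 Pharmacokinetic and Immunogenicity Analyses".

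The SAP 8.2.1 table has two areas: AUClast and AUCinf ("Area under drug concentration curve from time 0 extrapolated to infinity"). Protocol 9.1.3 also lists "Area under the serum concentration-time curve over the dosing interval" (AUC0-tau), AUC0-336 for nivolumab (for comparison with published two-weekly dosing) and the percentage of AUC extrapolated. None of these three is in the SAP table, and no reason is given. By contrast, SAP 3.2.4.2 does explain why the JTXP biomarker was dropped.

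**The concern.** CL is dose divided by AUCinf, and Vz and AUCinf/D use the same area. An area judged too uncertain to summarise as AUCinf would still enter the CL, Vz and AUCinf/D summaries for the same cohort. The AUCinf table would then describe only the faster-eliminating subjects, while the CL table described everyone who passed the λz condition.

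The limit also acts on half-life. Where a long half-life reflects slow clearance, the subjects removed are those with the highest exposure. Protocol 1.4.1 describes linear plus target-mediated clearance and non-linear PK in mice and rats. If half-life rises with dose, more subjects would be removed at higher doses. That would also distort the AUC0-∞ dose-proportionality regression in Protocol 9.5.3 if it used the filtered values.

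PK of JTX-2011 and of each partner drug is a secondary objective. AUClast remains, but it ends at each subject's last quantifiable sample, so it is not a fixed-interval AUC across Part A doses of 0.003 to 1 mg/kg.

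**Working it through.** The plan states no half-life limit, so there is no figure of its own to reproduce. The check asks what the 20% rule implies.

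Inputs from the documents:

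- Extrapolation limit: 20% (SAP 9.10.1).
- Profile length T: 21 days for three-weekly dosing (Protocol 1.4.2.1, "administered on a 21-day cycle"), ending at the C2D1 pre-dose sample; 42 days for JTX-2011 in Part E (Protocol 5.3).
- AUC method: "the estimation method will be linear up, linear down" (SAP 9.10.1).
- Day 8 and Day 15 PK samples in Parts A, B, E and G only (Protocol 7.2.4 and 7.2.5).

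Half-life, its variability and the split between clearance and volume are not given, so they are assumed below.

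**Step 1: shared area.** AUCinf = AUClast + Clast/λz, CL = dose/AUCinf, Vz = CL/λz. All depend on the same extrapolated term.

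**Step 2: half-life at which the limit bites.** For mono-exponential decline the extrapolated share is 2^(−T/t½). It exceeds 0.20 when t½ > T × ln 2/ln 5 = 0.4307 × T.

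- T = 21: 9.04 days. Shares are 12.5% at a half-life of 7 days, 23% at 10, 35% at 14 and 48% at 20.
- T = 42: 18.1 days.
- Last quantifiable sample at 14 days: 6.03 days.

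Numerical non-compartmental analysis (linear trapezoid, 1-hour infusion, last three points for λz) on a Part A-type schedule gives 9.12 days. With an assumed distribution phase (30-70% of initial concentration, half-life 1-2 days) it gives 9.5 to 11.3 days. The 42-day schedule gives 18.3 to 20.3 days.

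**Step 3: bias in the summarised mean AUCinf (T = 21).** Take CL and V as independent lognormal, with AUCinf = dose/CL and t½ = ln 2 × V/CL. Let a = ln(1 + CV_CL²), b = ln(1 + CV_V²), s = √(a + b) and z = ln(9.04/m)/s, where m is the median half-life. The proportion kept is Φ(z). The mean AUCinf of those kept, relative to all subjects, is Φ(z − a/s)/Φ(z).

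| Assumption | m (days) | z | Kept | Kept mean / full mean |
|---|---|---|---|---|
| CV of CL 30%, of V 20% (a = 0.0862, b = 0.0392, s = 0.354) | 7 | 0.724 | 77% | 0.684/0.765 = 0.89 |
| | 9 | 0.014 | 51% | 0.409/0.506 = 0.81 |
| | 12 | −0.799 | 21% | 0.149/0.212 = 0.70 |
| CV of half-life 40%, all through CL (a = 0.148, b = 0, s = 0.385) | 7 | 0.665 | 75% | 0.610/0.747 = 0.82 |
| | 9 | 0.013 | 51% | 0.355/0.505 = 0.70 |
| | 12 | −0.734 | 23% | 0.132/0.231 = 0.57 |

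Simulation gives the same ratios within rounding. With CV of CL 10% and of V 40%, the ratios at 7, 9 and 12 days are 0.989, 0.980 and 0.968. With no variation in CL they are 1.00, although a quarter to three quarters of subjects are removed.

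**Step 4: mismatch with CL.** Under the first set of assumptions, with AUCinf filtered and CL not, geometric mean AUCinf × geometric mean CL / dose is 0.91, 0.83 and 0.72 at medians of 7, 9 and 12 days. On identical subjects it is exactly 1.

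**The case against.** The case on the other side has several parts.

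- **The rule for CL and Vz is read from silence.** The SAP never says these parameters stay in when extrapolation exceeds 20%, and the AUCinf rule could be taken to include AUCinf/D. This stands, and is why the point is put as a literal reading. Nothing in the SAP extends the limit, however, and summarising is the default.
- **A reader might infer that every subject with a half-life above 9 days is lost.** That needs mono-exponential decline, a 21-day interval and a quantifiable C2D1 sample. In the three-weekly Phase 2 cohorts, which have no Day 8 or Day 15 sample, the three-point condition probably removes AUCinf and CL together. The sampling tables are too broken in the available text to settle this.
- **A reader might infer that AUCinf is necessarily biased low, or that CL would come from mostly extrapolated areas.** The first fails if half-life varies only through volume. The second needs a share above 50%, hence a half-life above 21 days on a 21-day profile.
- **A reader might infer that no comparable AUC is left.** When C2D1 is quantifiable, Cycle 1 AUClast is close to AUC over 0-21 days. It loses that property at doses or in subjects where late samples fall below quantitation.
- **Agreement between means would be imperfect anyway.** SAP 9.10.1 gives geometric means for Cmax and AUC parameters only. On identical subjects with lognormal CL, arithmetic mean CL × arithmetic mean AUC / dose is 1 + CV², or 1.09 at CV 30%. This stands. A common filter makes the subjects agree; adding a geometric mean for CL would let the product be checked.
- **The consequence is limited.** The number of subjects is printed for each parameter and excluded AUCinf values stay flagged in listings. SAP 3.2.4.1 bases selection of the recommended Phase 2 dose on target engagement. No stated decision uses the filtered AUCinf. This stands, and keeps the point below a critical one.

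**Conclusion.** The point holds as an inconsistency in the summary tables of a secondary objective, and should be corrected. As written, the 20% limit applies to AUCinf only, so AUCinf would be summarised on a different set of subjects from AUCinf/D, CL and Vz. The limit corresponds to a half-life of about 9 days for a mono-exponential 21-day profile, about 9.5 to 11.3 days with an assumed distribution phase, and about 18 to 20 days for six-weekly JTX-2011. Parts A, B, E and G are mainly concerned.

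The size cannot be fixed from the documents. At assumed median half-lives of 7 to 12 days, the summarised mean AUCinf is about 10-30% low (CV of CL 30%, of V 20%) or 18-43% low (CV of half-life 40%, all through clearance). It is near zero if half-life varies only through volume. The unexplained loss of AUC0-tau and nivolumab AUC0-336 is a separate, firm finding that needs no assumption.

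**What to change.** 1. In SAP 9.10.1, apply one extrapolation rule to AUCinf, AUCinf/D, CL and Vz in the summary tables. Print the number excluded by dose level and add an unfiltered sensitivity summary. The common rule restores consistency but still selects on clearance (CL of those retained would be biased high), so the counts and the unfiltered summary are needed with it.
2. In SAP 8.2.1 and 9.10.1, restore AUC0-tau as a summarised exposure for Cycle 1 of Parts A, B, E and G, taken over each drug's own dosing interval, and AUC0-336 for nivolumab in Part B. State how samples taken off nominal time or below quantitation are handled.

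The samples are already scheduled. The cost is a SAP update, a few more non-compartmental outputs, and fewer subjects in the filtered CL and Vz summaries.

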### **9.10.2 IMMUNOGENICITY ANALYSES**

ADA and NAb titers will be listed by subject. Titers will be summarized by Drug, Part, Treatment, Dose Level, Cycle and Timepoint. The within-cohort (ie by Drug, Part,

Treatment and Dose Level) incidence of ADA and NAb will be summarized using ADA Analysis Set.

ADA and NAb incidence will be presented across all time points on study and by each time point as described below:

- Overall incidence: the number and percentage of subjects that are ADA- or NAb-positive subjects at any point in the study. Each positive subject should be counted only once, regardless of the overall number of positive samples.
- Treatment-induced incidence: the number and percentage of the subjects with at least one positive post-treatment sample who were ADA-negative at baseline.
- Treatment-boosted incidence: the number and percentage of the subjects that were ADA-positive at baseline and have at least one post-treatment result with a higher titer than baseline.

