9.1.1. Safety Endpoints

The following safety endpoints will be assessed:

- Incidence and severity of treatment-emergent adverse events;
- Incidence and severity of treatment-emergent changes in clinical laboratory values;
- Incidence of dose limiting toxicities;
- Incidence of anti-drug antibodies to JTX-2011 and/or nivolumab, ipilimumab, or pembrolizumab;
- Incidence of neutralizing antibodies to JTX-2011 and/or nivolumab, ipilimumab, or pembrolizumab;
- Incidence of decreases in ECOG performance status;
- Incidence of clinically significant changes in ECG measurements.

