9.4.2. Analysis Set

All Subjects Set will include all subjects who have signed the informed consent and have subject numbers in the electronic clinical database.

The **Safety Population (SAF)** will include all subjects who have been treated with at least one dose of study drug (JTX-2011, nivolumab, ipilimumab, or pembrolizumab). The SAF will be the primary analysis set for all efficacy and safety analyses, unless otherwise specified.

Pharmacokinetic/Pharmacodynamic Analysis Set (PK/PD Set) will include all subjects who received at least one dose of the study drug and who provide at least one observation for at least one of the PK or PD endpoints without protocol violations that would be deemed by the trial pharmacokineticist to interfere with the PK or PD analysis.

Immunogenicity Analysis Set will include all subjects who received at least one dose of the study drug and provided one serum sample that could be successfully analyzed by both a screening and confirmatory validated ADA assay (for ADA analysis) or NAb assay (for NAb analysis).

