#### 6.1.1 SUBSETS OF THE SAF

- Response Evaluable Set: subjects in SAF who have a baseline tumor assessment, and either has at least one post-baseline tumor assessment scan and/or discontinued treatment due to death or disease progression.
- The DLT Evaluable Set: SAF subjects in Phase 1 parts (A, B, E, G) who receive at least one dose of JTX-2011 during the DLT-evaluation period (1st cycle) and complete the DLT-evaluation period (1st cycle) or experience any DLTs.
- Biomarker Analysis Set: SAF who have a baseline sample and at least one post treatment biomarker sample.
- ADA Analysis Set: SAF who have a baseline sample and at least one post treatment ADA sample.

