### 8.2.2 IMMUNOGENICITY

Immunogenicity endpoints include ADA and NAb incidence.

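### Treatment-boosted ADA is counted on any single titer above baseline with no minimum rise, so assay variability alone can produce boosted calls, more often in subjects with more samples (low severity)

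*SAP*

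**What the plan says.** Protocol 9.1.1 lists as a safety endpoint "Incidence of anti-drug antibodies to JTX-2011 and/or nivolumab, ipilimumab, or pembrolizumab". SAP 8.2.2 defines the endpoint no further: "Immunogenicity endpoints include ADA and NAb incidence".

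SAP 9.10.2 then splits incidence into three categories:

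- **Overall:** positive at any point in the study, each subject counted once.
- **Treatment-induced:** negative at baseline with at least one positive post-treatment sample.
- **Treatment-boosted:** "ADA-positive at baseline and have at least one post-treatment result with a higher titer than baseline".

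On timing, the section states that "ADA and NAb incidence will be presented across all time points on study and by each time point". The set used is the ADA Analysis Set (SAP 6.1.1): "SAF who have a baseline sample and at least one post treatment ADA sample". Titers are also listed by subject and summarized by cycle and time point.

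The footnotes to Protocol Tables 11 and 12 (Parts A and B, including the expansion cohorts) place ADA samples before dosing on Day 1 of every cycle and at End of Treatment.

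**The concern.** The threshold for being boosted is the subject's own single baseline reading. One later reading one dilution step higher is enough, whatever the other readings show. No minimum rise and no assay-precision margin appears in SAP 3.2.2, 6.1.1, 8.2.2 or 9.10.2, or in Protocol 9.1.1 or 9.4.2.

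The confirmatory assay in Protocol 9.4.2 does not fill the gap. Its immunogenicity set requires a sample that "could be successfully analyzed by both a screening and confirmatory validated ADA assay". That concerns whether a sample can be analyzed for ADA, not whether a rise in titer is real.

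At stake is how to read the boosted count. If repeat readings of an unchanged titer often differ by one step, the count includes subjects in whom nothing happened, and the chance of inclusion grows with the number of samples.

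The section also does not say whether the boosted percentage is taken over baseline-positive subjects or over the whole ADA Analysis Set. The two can differ greatly.

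**Working it through.** The plan gives no false-boost rate, so there is no figure to reproduce. The check asks how often the rule is met when the true titer does not change.

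**Inputs from the documents**

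- Rule: any post-treatment titer above the baseline titer (SAP 9.10.2).
- Minimum number of post-treatment samples k: 1 (SAP 6.1.1).
- Growth of k under the Table 11 and 12 schedule: a subject who starts c cycles gives c − 1 later Day 1 samples plus one at End of Treatment, so k = c if none is missed. Three cycles give k = 3.

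**Inputs assumed, because the documents do not give them**

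- Dilution series: 2-, 3- or 4-fold.
- Assay SD: 0.25 to 1.0 on the log2 titer, independent between samples.
- k from 1 to 8.

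**Formula.** Let the baseline reading B and each later reading X have the same distribution. Then

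P(called boosted, no true change) = 1 − Σ_b Pr(B = b) × Pr(X ≤ b)^k.

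**Hand check.** Let a reading be one step low with probability q, one step high with probability q, and otherwise correct. For q = 0.1 and k = 3:

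1 − [0.1 × 0.1³ + 0.8 × 0.9³ + 0.1 × 1] = 1 − [0.0001 + 0.5832 + 0.1] = 0.317.

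The same formula gives 0.170 for k = 1 and 0.475 for k = 6. If a two-step rise is required, baseline must read low and a later sample high: 0.1 × (1 − 0.9³) = 0.027 for k = 3.

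**Upper limit.** For a continuous titer without ties, baseline is the highest of k + 1 exchangeable readings with probability 1/(k + 1). The false-boost rate is then k/(k + 1): 50% for k = 1, 75% for k = 3, 89% for k = 8.

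**Normal error on a dilution grid** (simulation, 200,000 subjects per cell, random position of the true titer on the grid). Share of unchanged baseline-positive subjects called boosted under the SAP rule:

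| Dilution | SD (log2) | k = 1 | k = 3 | k = 8 |
|---|---|---|---|---|
| 2-fold | 0.25 | 14.1% | 25.6% | 36.9% |
| 2-fold | 0.5 | 25.6% | 45.4% | 62.5% |
| 2-fold | 1.0 | 36.4% | 60.4% | 77.8% |
| 3-fold | 0.25 | 8.9% | 16.3% | 23.3% |
| 3-fold | 1.0 | 29.8% | 51.2% | 69.1% |
| 4-fold | 0.25 | 7.0% | 12.9% | 18.5% |
| 4-fold | 0.5 | 14.0% | 25.7% | 37.1% |
| 4-fold | 1.0 | 25.9% | 45.3% | 62.6% |

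The range is 7.0% to 77.8%, and every row rises with k.

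**Alternative rules, 2-fold series**

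- Two-step minimum, SD 0.5: 2.5% (k = 1), 4.4% (k = 2), about 6% (k = 3), 7.3% (k = 4), 9.6% (k = 6).
- Two-step minimum, SD 1.0: 15.0% (k = 1) to 42.2% (k = 6). A fixed number of steps is not enough for an imprecise assay.
- Any rise at two consecutive samples, SD 0.5: 13.6% (k = 2), 22.7% (k = 4), 28.7% (k = 6). Repetition without a minimum rise helps less at this SD.

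**Effect of the denominator.** If the percentage is taken over the whole ADA Analysis Set, the part due to noise is baseline prevalence times the false-boost rate. Prevalence is not given. At assumed values of 2% and 10%, with a rate of 45%, it is 0.02 × 45% = 0.9% and 0.10 × 45% = 4.5%.

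**The case against.** The strongest reply is that little depends on this category.

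- **Overall incidence is untouched.** A baseline-positive subject is already counted as positive, boosted or not. Treatment-induced incidence covers only baseline-negative subjects. This stands, so the endpoint in Protocol 9.1.1 is not itself overstated.
- **The analysis is descriptive.** SAP 3.3.1 rules out formal hypothesis testing and SAP 7.10 rules out comparisons. This stands. A reader might infer that cohorts treated for longer will wrongly look more immunogenic. The SAP makes no such comparison, and longer exposure could also produce more real boosting.
- **The by-time-point display judges one sample at a time.** This stands in part. The count there does not accumulate over samples, but noise remains: the k = 1 column runs from 7.0% to 36.4%.
- **Few subjects may be baseline-positive.** This is plausible. JTX-2011 is first-in-human, and exclusion criteria 5 and 8 remove some subjects with known antibodies. No prevalence is stated, so the number cannot be settled.
- **Titers are listed, so a stricter rule could be applied later.** True, but that threshold would then be chosen with the titers in view.
- **A plain 4-fold rule changes nothing on a 4-fold series**, where it is a single step. This stands, and the threshold must be set in dilution steps and tied to assay precision.

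**Conclusion.** The point holds at low severity. The rule sets no minimum rise, and in the across-all-time-points summary its false-boost rate increases with the number of samples. Under the assumptions stated, that rate among baseline-positive subjects lies between about 7% and 78%. The direction follows from the rule; the size rests on dilution factor, assay SD and sample count, none of which the documents give.

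Two stronger readings are not supported:

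- **That noise classes about a third to a half of baseline-positive subjects as boosted.** That is reached in only part of the range, for example 2-fold dilutions with SD about 0.35 to 0.5 and 2 to 4 samples (29% to 51%).
- **That the boosted count mostly measures noise.** The calculation sets the true effect to zero, so it gives the error rate among unchanged subjects. The share of the observed count that is noise also depends on the true boost rate, which is unknown.

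**What to change.** Before database lock, amend the definition in SAP 9.10.2. A subject is treatment-boosted if ADA-positive at baseline with at least one post-treatment titer that is two or more dilution steps above baseline (4-fold on a 2-fold series), or above the assay's validated minimum significant ratio if that is larger. State the denominators as well: boosted among baseline-positive subjects, treatment-induced among baseline-negative subjects. The dilution factor and the ratio should be taken from the assay validation and written into the SAP.

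The cost is one or two sentences and the renewed sign-off that SAP section 2 requires for updates. No new data are needed. The loss is that true one-step rises are not counted. On a coarser series this loss is larger, because two steps mean 3² = 9-fold or 4² = 16-fold. Listed titers still show such subjects individually.
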